This is an open-label, single-arm, pilot study on the effects of topical imiquimod treatment in preventing keloid recurrence after surgical excision. Keloids are abnormal scars that form in certain genetically predisposed individuals following trauma to the skin. They can be physically disabling and cause social impairment. Many therapies have been proposed and trialed for the permanent removal of keloids, but they all have limited efficacy. (1)

Topical imiquimod therapy has been reported to decrease keloid recurrence following keloidectomy in human patients (8-13). In our lab, we observed that topical imiquimod pre-treatment (imiquimod initiated prior to onset of trauma) improves wound closure and decreases scar formation in mouse ear-punch models of wound healing. Given all previous reports of adjuvant imiquimod therapy to keloidectomy initiated imiquimod therapy after keloidectomy, we would like to test the efficacy of topical imiquimod pre-treatment in preventing keloid recurrence after surgical excision.

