1.1 Background

Keloids are benign dermal fibroproliferative tumors that represent a form of abnormal wound healing following any insult to the deep dermis, including lacerations, abrasions, surgery, piercings, vaccinations, and burns in predisposed individuals (1). They are distinguished from hypertrophic scars, another type of abnormal scar formation, by their extension beyond the borders of the original wound, failure to regress spontaneously, and tendency to recur following excision (1).

Keloids tend to occur more frequently in dark-skinned individuals, with an incidence of up to 16% in those of black and Hispanic backgrounds (2). These lesions appear to affect male and female subjects equally and most commonly occur in persons aged 10-30 years (2). They typically form on the ears, face, chest, and shoulders and can cause pain, burning, itching, and restriction of motion. Furthermore, the scars can be extremely disfiguring and potentially cause significant social and psychological distress in affected individuals.

The process by which keloids develop is poorly understood, though most theories of keloid etiology relate to fibroblast dysfunction (2). These lesions are difficult to treat, as they frequently recur following excisional removal. Current treatment options include surgical excision, laser, intralesional injections, pressure and silicone dressings, topical preparations, oral agents, radiation, and cryotherapy (1). Oftentimes, surgical excision is combined with adjuvant therapies such as corticosteroids and immunomodulators at the time of skin closure because surgical excision alone has recurrence rates ranging between 45% and 100% (3). Additionally, because surgical excision requires complete removal of all abnormal tissue, post-excision keloid recurrence may lead to a larger keloid than prior to excision. Although many adjuvant therapies to surgical excision and modalities for keloid removal have been proposed, there has been no consensus regarding how to best treat these lesions, and there is currently no medication approved for the indication of reducing keloid recurrence after excision.

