1.4 Clinical Data to Date

Case series and prospective trials of 5% Imiquimod after surgical keloidectomy have been reported. However, the results have been variable. As summarized in **Table 1**, post-excision treatment with Imiquimod appears to be most effective in preventing recurrence of keloids on the ears but has limited efficacy in other locations. Additionally, some studies were limited by poor patient follow-up compliance.

All of the reported studies were designed such that Imiquimod was started after surgical excision of keloids. There are no reports of initiating Imiquimod prior to surgical excision, and our preclinical data suggests that there may be a benefit to pre-excision Imiquimod therapy.

Table 1 Summary of published clinical data for Imiquimod therapy post-keloidectomy

Reference study	Number of keloids	Sites treated	Recurrence (%)	Follow-up duration
Berman (2002) (8)	11 (10 patients)	Earlobe (10) and back (1)	0 (0%)	24 weeks
Martin-Garcia (2005) (9)	8 (6 patients)	Earlobe	2 (25%)	24 weeks
Stashower (2006) (10)	8 (4 patients)	Earlobe	0 (0%)	12 months
Maholtra (2007) (11)	3 (2 patients)	Presternal	3 (100%)	12 weeks
Cacao (2009) (12)	9 (9 patients)	Trunk	8 (89%)	12 weeks
Frias (2018) (13)	41 (25 patients)	Trunk (9), suprapubic (2), extremity (4), auricular (20)	9 trunk (100%), 0 suprapubic (0%), 4 extremity (100%), 3 auricular (15%)	6 months

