4.1 Inclusion Criteria

1. Age \geq 18
2. Men and women who present clinically with keloids requesting excision
3. Any number of keloids
4. Keloid no larger than 5cm in diameter at the base
5. Clinical findings consistent with keloid formation, including: a scar that does not spontaneously regress, extends beyond borders of normal tissue, may be pruritic, may be painful.
6. Location of keloid in low-risk areas – areas other than above the neck, hands, feet, or groin
7. Able and willing to give informed consent

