7.1 Sample Size Determination

In this open-label, single-arm pilot study, 10 patients will be enrolled.

The sample size calculation was based on a historical recurrence rate of 70% at 8 week follow-up after excision alone and an expected 25% recurrence rate with Imiquimod treatment. Using 80 % power and $\alpha = 5\%$, the estimated sample size required is 8. Allowing for a withdrawal rate of approximately 20 %, 10 subjects will have to be enrolled.

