7.3 Subject Population(s) for Analysis

All subjects who completed the study protocol will be included in the study analysis.

8 Safety and Adverse Events

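### The stated 80% power is 68% by exact calculation with the planned 8 evaluable patients, the 25% input has no source and no trunk or extremity series near it, and the single arm cannot isolate pre-treatment

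*Combined protocol and SAP*

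**What the plan says.** Section 7.1 takes a "historical recurrence rate of 70% at 8 week follow-up after excision alone and an expected 25% recurrence rate with Imiquimod treatment". At 80% power and α = 5% it concludes that "the estimated sample size required is 8", and raises this to 10 for about 20% withdrawal. It names no test or sidedness and cites no source for either rate.

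Section 7.2 plans a response percentage with a 95% confidence interval (CI). It gives no CI method, benchmark or success rule. Section 7.3 analyses completers: "All subjects who completed the study protocol will be included in the study analysis".

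Eligible keloids lie in "areas other than above the neck, hands, feet, or groin" (Section 4.1), so ears are out. Section 1.4 reads Table 1 as showing that "post-excision treatment with Imiquimod appears to be most effective in preventing recurrence of keloids on the ears but has limited efficacy in other locations", and adds: "All of the reported studies were designed such that Imiquimod was started after surgical excision of keloids".

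Section 1 gives the aim: "we would like to test the efficacy of topical imiquimod pre-treatment in preventing keloid recurrence after surgical excision". Section 3.2 ties the primary endpoint to starting before excision. Under Sections 5.2 and 6.1 each patient applies cream for 1 week before and 5 weeks after surgery.

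**The concern.** There are three linked problems.

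- **Power.** A normal approximation is unreliable with 8 patients, where the achievable error rates move in large steps. If the 80% is overstated, the trial is more likely than its readers think to be inconclusive even when the treatment works as hoped.
- **Inputs.** The 25% drives the sample size, yet the protocol's own table shows nearly universal recurrence in the series at eligible sites.
- **Conclusion.** The stated aim is to test pre-treatment, but the design compares a six-week regimen spanning surgery with excision alone. A good result could be credited to the pre-excision week when it came from the weeks after surgery.

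Because Section 7.2 fixes no CI method, the reading of a borderline result could also be chosen after the data are seen.

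**Working it through.** **Inputs.** From Section 7.1: null recurrence p0 = 0.70, alternative p1 = 0.25, α = 5%, power 80%, withdrawal 20%. Evaluable patients: 10 × 0.8 = 8, which matches the completers-only analysis in Section 7.3.

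**1. The plan's figure.** One-sample normal approximation, two-sided:

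n = [(1.960·√(0.70·0.30) + 0.842·√(0.25·0.75)) / 0.45]² = 7.87, rounded up to 8.

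The stated 8 is reproduced. The one-sided version gives 6.17, that is 7.

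**2. Exact error rate at n = 8, p = 0.70.**

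- P(X ≤ 2) = 0.3⁸ + 8·0.7·0.3⁷ + 28·0.7²·0.3⁶ = 0.0113
- P(X ≤ 3) = 0.0113 + 56·0.7³·0.3⁵ = 0.0580

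Allowing 3 recurrences breaks the 5% limit even one-sided. The cutoff is therefore 2, one- or two-sided.

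**3. Exact power at n = 8, p = 0.25.**

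P(X ≤ 2) = 0.75⁸ + 8·0.25·0.75⁷ + 28·0.25²·0.75⁶ = 0.679.

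The chance of missing is 1 − 0.679 = 32%, against the planned 20%.

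**4. Other numbers and true rates.** The 40% and 50% columns are illustrative assumptions, not figures from the protocol. Two-sided means equal tails, which is the same rule as a Clopper-Pearson 95% CI lying wholly below 70%.

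| Evaluable, rule | Cutoff | Lower-tail size | Power at 25% | at 40% | at 50% |
|---|---|---|---|---|---|
| 8, one- or two-sided | 2 | 0.011 | 68% | 32% | 14% |
| 9, two-sided | 2 | 0.004 | 60% | – | – |
| 9, one-sided 5% | 3 | 0.025 | 83% | – | – |
| 10, two-sided | 3 | 0.011 | 78% | 38% | 17% |
| 10, one-sided 5% | 4 | 0.047 | 92% | 63% | 38% |
| 11, two-sided | 4 | 0.022 | 89% | – | – |

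Exact 80% power therefore needs 9 evaluable one-sided (9/0.8 = 11.25, enrol 12) or 11 two-sided with equal tails (11/0.8 = 13.75, enrol 14).

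**5. Effect of the CI method.**

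| Result | Clopper-Pearson | Wilson |
|---|---|---|
| 2/8 | 3.2% to 65.1% | 7.1% to 59.1% |
| 3/8 | 8.5% to 75.5% | 13.7% to 69.4% |

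At 3/8 the exact interval includes 70% and the Wilson interval excludes it. If the true rate is 25%, 3/8 has probability 0.208.

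**6. Table 1 at eligible sites.** Recurrence was 3/3 presternal, 8/9 trunk, 9/9 trunk and 4/4 extremity. The exceptions are one back lesion (0/1, in a mainly earlobe series) and two suprapubic lesions (0/2). The only row showing 25% is an earlobe series (2/8). Counts are per keloid, treatment was post-excision only, and follow-up was 12 weeks or longer. In the largest series the listed sites add to 9 + 2 + 4 + 20 = 35, against 41 keloids stated.

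**7. The 70%.** It lies inside the 45% to 100% cited in Section 1.1 for excision alone, but that range gives no site or time point.

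**The case against.** The strongest reply is that 68% depends on a test the plan never named. The stated 8 reproduces. The Wilson interval, which fits the plan's type of approximation, would accept 3/8 and give 88.6% power. That is correct, but its lower-tail error is then 5.8%, above the plan's own 5%. Any non-randomised rule that keeps 5% stops at 2 of 8. What stands is that the plan made no arithmetic slip: it used an approximation unsuited to 8 patients.

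Exact power is also saw-toothed. With 9 evaluable, allowing 3 recurrences gives 83% power one-sided, and also under the minimum-likelihood two-sided exact test. It misses the equal-tails rule narrowly (size 0.0253 against 0.025), and under that rule power is 60%. So the requirement of 11 holds for equal tails only, and the 9-patient case should be reported.

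On inputs, the protocol already calls 25% expected and concedes limited efficacy away from the ears. It also gives a reason to hope for better, since no earlier study began before excision. This is fair: Table 1 does not disprove 25%. It means only that no trunk or extremity series in the table supports it.

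On design, not separating components is inherent in a declared single-arm pilot, and the primary objective in Section 2 refers to imiquimod cream generally. Excision alone is a usable benchmark for the whole regimen. But Sections 1 and 3.2 frame the question as pre-treatment, so the limit on the conclusion needs stating.

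**Conclusion.** The concern holds. On the plan's own rates and its own 8 evaluable patients, exact power is 68%, 12 points below the claim. This assumes a test that keeps error at or below 5%. If all 10 complete, power is 78% with equal tails or 92% one-sided. Power falls quickly if the effect is smaller than hoped: with 8 patients it is 32% at an assumed 40% recurrence and 14% at 50%.

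Both rates are unsourced assumptions, and the trunk and extremity evidence shown does not support 25% at 8 weeks. A favourable result would describe the combined regimen, not the effect of starting early. Even the target result of 2/8 would exclude 70% but not the 45% at the bottom of the cited excision-alone range. None of this invalidates a 10-patient pilot, but the power statement is wrong as written and should be corrected.

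**What to change.** 1. **Section 7.1.** Keep 10 patients. State the test and sidedness. Replace the 80% claim with exact power (two-sided, equal tails): at a true 25%, 68% with 8, 60% with 9 and 78% with 10; at an assumed 40%, 32% with 8 and 38% with 10; at an assumed 50%, 14% and 17%. Label 70% and 25% as assumptions, and say that no trunk or extremity series in Table 1 supports 25%.
2. **Section 7.2.** Prespecify a Clopper-Pearson 95% CI for the recurrence rate, and name 70% at week 8 as the assumed benchmark, kept distinct from the week-12 phone assessment. Add that the cited excision-alone range is 45% to 100%, so 2/8 (3% to 65%) would exclude 70% but not 45%, and 3/8 (9% to 76%) would exclude neither.
3. **Sections 3.2 and 7.2.** Limit conclusions to the combined pre- plus post-excision regimen, and state that the design does not isolate pre-treatment.
4. **Table 1, if used for context.** Show counts by site without a pooled CI. Note that they are per keloid, post-excision only and at 12 weeks or longer, and check the 35-versus-41 count first.

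The cost is wording, with no new patients, visits or data. The price is a less favourable power statement and a narrower claim about pre-treatment. Keeping a true 80% claim would need about 12 enrolled (one-sided) or 14 (two-sided, equal tails), which is not proposed for this pilot.

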Because the effects of the drug are not well studied in pregnancy and during breastfeeding, it is possible that there are harmful side effects that are not yet known to both the mother and unborn or breast-feeding child. Therefore, pregnant and breastfeeding subjects are excluded from the study. Additionally, the risks of this study includes risks of breach of confidentiality. While every effort will be made to protect the confidentiality of study subjects, there is a potential risk of an inadvertent or unintended breach of confidentiality.

As demonstrated in patients who have used 5% Imiquimod for other FDA approved indications, risks of topical application of 5% imiquimod are minimal. Additionally, previous studies as well as our preclinical data indicates that 5% imiquimod could modulate wound healing and prevent keloid recurrence in patients when applied prior to keloid-excision and continued after the procedure. Therefore, we believe that the benefit of possible decrease in keloid recurrence outweighs the minimal risks posed by topical 5% imiquimod therapy.

2 Study Objectives

Primary Objective

To assess the efficacy of 5% Imiquimod cream on preventing keloid recurrence after excision. Subjects will be evaluated by a consultant dermatologist at 2, 4, and 8 weeks following excision and by phone 12 weeks after excision to assess for clinical evidence of lesion recurrence.

[figure not shown]
Secondary Objectives

To assess the safety and tolerability of 5% Imiquimod in subjects undergoing keloid excision. Subjects will be evaluated by a consultant dermatologist at 2, 4, and 8 weeks following excision to assess for local site reaction such as redness, discomfort, swelling, and ulceration.

3 Study Design

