7.2 Statistical Methods

Response rate will be presented as a percentage, with 95% confidence intervals. Other endpoints will be presented descriptively, with an appropriate measure of variation (e.g. standard deviation) if necessary. Patient demographics will be summarized.

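### With 8 evaluable patients no cut-off delivers both 80% power and 5% error: the exact choices are 67.9% power at 1.1% error or 88.6% power at 5.8% error

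*Combined protocol and SAP*

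**What the plan says.** Section 7.1 (Sample Size Determination) bases the calculation on a "historical recurrence rate of 70% at 8 week follow-up after excision alone and an expected 25% recurrence rate with Imiquimod treatment". At 80% power and alpha 5% it concludes that "the estimated sample size required is 8". It continues: "Allowing for a withdrawal rate of approximately 20 %, 10 subjects will have to be enrolled". It does not state the test, the formula, the sidedness or a success cut-off.

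Section 7.2 (Statistical Methods) gives the planned analysis: "Response rate will be presented as a percentage, with 95% confidence intervals". It names no interval method and does not mention the 70% benchmark. Section 7.3 defines the analysis set: "All subjects who completed the study protocol will be included in the study analysis".

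Two other places affect what is being counted. Section 4.1 admits patients with "Any number of keloids", and Section 2 adds an assessment "by phone 12 weeks after excision to assess for clinical evidence of lesion recurrence", whereas 7.1 works at 8 weeks.

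**The concern.** With only 8 patients the recurrence count can take just nine values, so error and power move in large steps and a normal-approximation formula can promise a combination that no actual cut-off delivers. The stated power and alpha are the justification for the sample size. If they cannot both hold at the number the plan expects to analyse, the reader is misinformed about either the chance of missing the assumed effect or the chance of a false positive.

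Because 7.2 names no test or interval, the plan also does not say which of the two is given up. A result on the boundary could then be called a success or a failure after the data are known.

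**Working it through.** **Inputs, all from Section 7.1.** Historical recurrence p0 = 0.70; expected recurrence p1 = 0.25; power 80%; alpha 5%, sidedness not stated; 8 evaluable; withdrawal about 20%. Each patient is taken to contribute one result.

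**Step 1: reproduce the plan's figure.** One-sample proportion, normal approximation, two-sided 5%:

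n = [(1.96·√(0.70·0.30) + 0.8416·√(0.25·0.75)) / (0.70 − 0.25)]² = 7.87, rounded up to 8.

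Nominal power at n = 8: Φ[(0.45·√8 − 1.96·√0.21) / √0.1875] = 80.7%.

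Enrolment: 8 / (1 − 0.20) = 10. Both of the plan's numbers reproduce, so 8 is not a slip.

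**Step 2: exact binomial at n = 8.** Success is declared at x or fewer recurrences. Error is P(X ≤ x) at 70%; power is P(X ≤ x) at 25%.

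| Success if at most | Error | Power |
|---|---|---|
| 1 of 8 | 0.1% | 36.7% |
| 2 of 8 | 1.1% | 67.9% |
| 3 of 8 | 5.8% | 88.6% |
| 4 of 8 | 19.4% | 97.3% |

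No row has error at or below 5% together with power of at least 80%. Sidedness does not help: at 3 of 8 the lower tail alone is already 5.8%. The two-sided exact p-value, summing all outcomes no more likely than the one observed, is also 0.058.

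The approximate test itself rejects at 3 of 8: z = (0.375 − 0.70) / √(0.21/8) = −2.006. Its true error is therefore 5.8%.

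**Step 3: smallest n that meets both targets.**
- One-sided 5%: n = 9, at most 3 (error 2.5%, power 83.4%).
- Lower tail held to 2.5%: n = 11, at most 4 (error 2.2%, power 88.5%).

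**Step 4: what the interval in 7.2 would say at 3 of 8.** The upper 95% limit is:
- Wilson: 69.4%, which excludes 70%.
- Wald: 0.375 + 1.96·√(0.375·0.625/8) = 71.0%, which does not.
- Clopper-Pearson: 75.5%, which does not.

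The ambiguity remains with full retention: at 4 of 10 the limit is 68.7% by Wilson and 73.8% by Clopper-Pearson.

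**Step 5: how likely is a small evaluable number?** If each of 10 patients withdraws independently with probability 20% (an assumption), fewer than 8 are evaluable with probability 32%. The table under the fix therefore starts at 7.

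**The case against.** The strongest reply is that the formula giving 8 uses the null variance and so corresponds to the score test, whose interval is Wilson. That test rejects at 3 of 8 and does not reject at 8 of 8 (Wilson lower limit 67.6%). On this reading true power is 88.6%, above the target, and the whole defect is 0.8 percentage points of error. The 70% benchmark is itself uncertain: Section 1.1 gives 45% to 100% for excision alone, and the error of the 3-of-8 rule is 4.4% if the true rate is 72%, 10.6% at 65% and 47.7% at 45%. Finally, this is a pilot with a descriptive analysis and no go/no-go rule, so no planned decision carries either error.

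Much of this is fair. Eight is a correct approximate result, the excess error on the score-test reading is small, and uncertainty about 70% matters more than 0.8 points, though it is a separate question. But the plan does not say that it uses the score test or Wilson. A reader who applies an exact test or Clopper-Pearson gets 67.9% power. And although 7.2 is descriptive, 7.1 makes an explicit claim about power and alpha and rests the sample size on it. If no comparison is intended, that claim should not be there.

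**Conclusion.** The concern holds. At the plan's own expected evaluable number, the stated 80% power and 5% alpha are not jointly attainable. Either the assumed effect is missed 32% of the time (100% − 67.9%) rather than the stated 20%, or error is 5.8% rather than 5%.

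The shortfall is specific to 8 (and to fewer: at 7, the best rule within 5% has 75.6% power). With 9 or 10 evaluable patients a one-sided 5% exact test meets both targets; a rule holding the lower tail to 2.5% does not until 11. Enrolment of 10 and the planned estimate can stand. For a pilot this should be fixed, but it is no more serious than that.

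The figures take 70% and 25% as given and assume one independent result per patient at 8 weeks. They also assume that being evaluable is unrelated to outcome. The completers-only set in 7.3 may not satisfy that, which is a separate matter.

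**What to change.** Keep 10 enrolled. In 7.1, replace the claim about 8 patients with exact error and power for one rule chosen before data are seen, and name the same test or interval in 7.2. The options below show the largest number of recurrences counted as success, with (error, power):

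| Evaluable | One-sided 5% exact test against 70% | Wilson 95% upper limit below 70% | Clopper-Pearson 95% upper limit below 70% |
|---|---|---|---|
| 7 | 2 (2.9%, 75.6%) | 2 (2.9%, 75.6%) | 1 (0.4%, 44.5%) |
| 8 | 2 (1.1%, 67.9%) | 3 (5.8%, 88.6%) | 2 (1.1%, 67.9%) |
| 9 | 3 (2.5%, 83.4%) | 3 (2.5%, 83.4%) | 2 (0.4%, 60.1%) |
| 10 | 4 (4.7%, 92.2%) | 4 (4.7%, 92.2%) | 3 (1.1%, 77.6%) |

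State that the count is one result per patient at 8 weeks. If the 12-week phone result or a per-keloid count is meant, the figures must be redone. If no comparison with 70% is intended, delete the power claim and present the study as estimation only.

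The cost is wording in 7.1 and 7.2, with no extra patients. Each rule has something to disclose: the exact test has lower power at 8 than now stated, Wilson has 5.8% error at 8, and Clopper-Pearson stays below 80% power throughout 7 to 10 evaluable patients.

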7.2 Statistical Methods

Response rate will be presented as a percentage, with 95% confidence intervals. Other endpoints will be presented descriptively, with an appropriate measure of variation (e.g. standard deviation) if necessary. Patient demographics will be summarized.

